6.1 Objective

Evaluate the safety of vaccination through 28 days after the last vaccination with: **C1C62-M3M4 and C62-M4** in PWH on ART.

6.2 Endpoint Analysis

Outcome (Primary Safety Event): Occurrence of at least one ≥ Grade 3 Adverse Event (AE) including signs/symptoms, lab toxicities, and/or clinical events that are possibly or definitely related to study treatment from the first day of treatment (D0) through 28 days following the boost vaccination or D56.

NOTE: The occurrence of a Grade 3 elevated blood pressure during a study-related leukapheresis that resolves following completion of the procedure will not be included as a primary safety endpoint.

The probability of a primary safety event (≥ Grade 3 AE) from D0 through D56 (or 28 days following the second vaccination) will be estimated with a proportion and corresponding one-sided exact binomial 95% upper confidence limit.

The following tables of AE data will be created to summarize the number and percent of participants who experience at least one event of each of the following types:

- 1) Study treatment-related AEs by severity grade
- 2) All SAEs (this may be a listing if there are few events)
- 3) Study treatment-related SAEs
- 4) Fatal AEs (this may be a listing if there are few events)
- 5) AEs that result in study discontinuation or study treatment discontinuation
- 6) AEs categorized as AESI
- 7) AEs with severity Grade 3 or greater
- 8) Study treatment-related AEs with severity Grade 3 or greater
- 9) All treatment-related AEs with severity Grade 1 or greater

All of these tables will be generated for analysis reporting purposes.

7 Secondary Outcome: Safety

7.1 Objective

Evaluate the safety of vaccination through the end of study

7.2 Endpoint Analysis

Outcome (Secondary Safety Event): Occurrence of any ≥ Grade 1 AE including signs/symptoms, lab toxicities, and/or clinical events, that is possibly or definitely related to study treatment any time from the first day of treatment (D0) through D196 (Week 28).

NOTE: The occurrence of a Grade 3 elevated blood pressure during leukapheresis that resolves following completion of the procedure will not be included as a secondary safety endpoint. Safety data will include local and systemic signs and symptoms, laboratory measures of safety/toxicity, and all adverse and serious adverse events. Safety data will be routinely collected throughout the study.

Analysis: The probability of a secondary safety event (≥ Grade 1 AE) from D0 through D196 will be estimated with a proportion and corresponding one-sided exact binomial 95% upper confidence limit.

NOTE: Safety events include incidence and grade of all reportable unsolicited and solicited adverse events including SAEs, MAAEs, and AESIs post first dose of C1 and/or C62 through Day 196.

8 Secondary Outcomes: Immunological and Virologic Analysis

8.1 Objectives

Compare the within-participant relative change in magnitude of HIV-1-specific T cell responses following vaccination with **C62-M4** or **C1C62-M3M4**.

Compare the between-arm change in breadth of HIV-1-specific T cell responses following vaccination **C62-M4** or **C1C62-M3M4**.

8.2 Endpoint Analysis

The focus of our secondary immunologic objectives is to examine the effect of vaccination on both within-and between-participant T-cell magnitude and between-arm breadth of HIV-specific T cell responses.

Outcome 1 (T-Cell Magnitude): Relative changes in magnitude of T-cell responses to HIV-1 conserved regions measured by ex vivo IFN- γ ELISpot from pre-vaccination (one or more of

screening, enrolment, pre-vaccination leukapheresis or Day 0) to post-vaccination on Days 35 and 42.

This outcome consists of the following eight components:

Outcome 1.1: Relative change in magnitude of T-cell response to Mosaic-1 from prevaccination to Day 35 within each vaccinated arm.

Outcome 1.2: Relative change in magnitude of T-cell response to Mosaic-1 from prevaccination to Day 35 between vaccinated arms.

Outcome 1.3: Relative change in magnitude of T-cell response to Mosaic-2 from prevaccination to Day 35 within vaccinated arm.

Outcome 1.4: Relative change in magnitude of T-cell response to Mosaic-2 from prevaccination to Day 35 between vaccinated arms.

Outcome 1.5: Relative change in magnitude of T-cell response to Mosaic-1 from prevaccination to Day 42 within vaccinated arm.

Outcome 1.6: Relative change in magnitude of T-cell response to Mosaic-1 from prevaccination to Day 42 between vaccinated arms.

Outcome 1.7: Relative change in magnitude of T-cell response to Mosaic-2 from prevaccination to Day 42 within vaccinated arm.

Outcome 1.8: Relative change in magnitude of T-cell response to Mosaic-2 from prevaccination to Day 42 between vaccinated arms.

Analysis: Each of outcomes 1.1-1.8 will be analyzed separately. The magnitude of ex vivo ELISpot response will be examined using the log2 fold change of the quantified ELISpot response between the average of baseline visits and Day 35 and Day 42.To evaluate changes in magnitude from baseline (pre-vaccination) to post-boost vaccination (D35 and D42), the

relative change within participants will be estimated using a geometric mean ratio (GMR, also known as fold change) and evaluated with an exact two-sided Wilcoxon signed-rank test for within-arm comparisons and an exact two-sided Wilcoxon rank-sum test for between-arm comparisons. The Wilcoxon signed-rank test assumes symmetry of the change in natural log-transformed summed HIV-1 specific T cell response (estimated by GMR) under the null. If this assumption is violated, then a sign test will be conducted as a sensitivity analysis.

Outcome 2 (T-Cell Breadth): Change in breadth (difference in the number of ex vivo reactive/positive P076, PP077, PP078, PP079, PP080 subpools pre- and post-vaccination) of T-cell responses targeting HIV-conserved regions from pre-vaccination (one or more of screening, enrolment, pre-vaccination leuk, Day 0) to post-vaccination (Day 56).

This outcome consists of the following two components:

Outcome 2.1: Change in breadth of T-cell responses from pre-vaccination to post-vaccination (Day 56) within vaccinated arm.

Outcome 2.2: Comparison of change in breadth of T-cell responses from pre-vaccination to post-vaccination (Day 56) between vaccinated arms.

Analysis: Breadth is measured as the number of ex vivo reactive subpools (P076, PP077, PP078, PP079, PP080). To evaluate change in breadth in the number of T cell responses targeting HIV-conserved regions from baseline (pre-vaccination) to post-vaccination (D56), an exact two-sided Wilcoxon signed-rank test will be used for within-arm comparisons and an exact two-sided Wilcoxon rank-sum test will be used for between-arm comparisons.

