2.2.3 The Immunogens

2.2.3.1 Rationale for Design of HIVconsX

[figure not shown]
HIVconsX is was designed in silico using full-genome sequences of group M HIVs in the Los Alamos National Laboratory HIV Sequence Database (LANL-HSD), as of September 2013 (54). HIVconsX is comprised of six conserved regions of the Gag (region 1 and 2) and Pol (regions 3-6) of HIV computed into two complementary amino acid sequences, Mosaic-1 and Mosaic-2 (Figure 1A). Mosaic-1 and -2 differ in about 10% of amino acids and between them, maximize the match of the vaccine to the global circulating HIV-1 isolates (Figure 1B). Each of the four vaccines in this study uses a different order of the six conserved regions to minimize induction of T cell responses to potential newly formed and, therefore, irrelevant non-HIV epitopes generated by joining two adjacent regions together (Figure 1C).

The six regions in Gag and Pol in HIVconsX contain a high number of previously identified CD8⁺ T cell epitopes against HIV, restricted by 84 different HLA I alleles (54). These regions maximize epitopes associated with control of HIV viremia and minimize epitopes associated with poor HIV control (55). The conserved nature of these regions not only increase the likelihood of a match between the immunogens and infecting virus/es but also decreases the effects of virus escape, including pre-existing escape in the HIV reservoir (52).

The potential immunogenicity and efficacy of HIVconsX has been tested in cohort studies. First in a cohort of treatment naïve PWH, higher magnitude and breadth of CD8⁺ T-cell responses reactive to HIVconsX-derived peptides correlated with higher CD4⁺ T-cell count and lower viral load (54). More recently, our group used empirical methods to identify whether virus variants in the HIV reservoir could escape circulating T cell responses in PWH on ART. Epitope mapping and HIV sequencing of a cohort of 25 PWH on ART, found that 32% of T cell epitopes harbored escape variants in the HIV reservoir (50). On average, participants's T cells targeted 3 epitopes within HIVconsX (0-6), suggesting that therapeutic vaccination of HIVconsX will successfully increase circulating HIV-specific T cell responses (50). Importantly, T cell escape in regions corresponding to HIVconsX was 2.5-fold lower than escape outside of the immunogen (15.3% vs 43.5%) (50).

[figure not shown]

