10.7.4.4 Power Calculations for T cell Breath

Baseline HIV-specific T cell breadth from durably-suppressed PWH were used to inform power calculations (50). In this study, reactive HIV T cell epitopes in the HIV proteome (Clade B consensus and autologous reservoir virus) were defined in 25 PWH on ART.

For the **C62-M4** and **C1C62-M3M4** arms, we anticipate that vaccination will induce a change of breadth (the detection of a new reactive T cell epitope) ranging from 0-3 epitopes and 2-6 epitopes, respectively.

- We anticipate that **C62-M4** will induce a change in breadth with the following frequency distribution: 0 (20% of participants), 1 (50%), 2 (20%), and 3 (10%).
- We anticipate that **C1C62-M3M4** will induce a change in breadth with the following frequency distribution: 2 (30% of participants), 3 (40%), 4 (15%), 5 (10%), and 6 (5%).

Given these assumptions, n=8 evaluable participants per treatment arm provides 95% power to detect a difference between arms using an exact two-sided Wilcoxon rank-sum test (at a 0.05 significance level).

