| G1 (MOS1+MO S2) | PP076 | 18mer peptides overlapping (64) by 11aa spanning G1 of both Mosaic-1 and Mosaic-2 | 2ug/ml | 4 | Examining breadth at the subpool level. Also, a second an independent check of Mos-1/Mos-2 data. Specifically, we expect any changes in Mos-1- or Mos-2-specific T cell responses to be reflected in changes at the sub-pool level. | Secondary: Breadth (0-5) |
| G2_P4 P5 (MOS1+MO S2) | PP077 | 18mer peptides overlapping (38) by 11aa spanning G2, P4 and P5 of both Mosaic-1 and Mosaic-2 | 2ug/ml | 4 | Examining breadth at the subpool level. Also, a second an independent check of Mos-1/Mos-2 data. | Secondary: Breadth (0-5) |
| P3-A (MOS1+MO S2) | PP078 | 18mer peptides overlapping (42) by 11aa spanning the 5` half of P3 of both Mosaic-1 and Mosaci-2 | 2ug/ml | 4 | Examining breadth at the subpool level. Also, a second an independent check of Mos-1/Mos-2 data. | Secondary: Breadth (0-5) |

| P3-B (MOS1+MO S2) | PP079 | 18mer peptides overlapping (54) by 11aa spanning the 5` half of P3 of both Mosaic-1 and Mosaic-2 | 2ug/ml | 4 | Examining breadth at the subpool level. Also, a second an independent check of Mos-1/Mos-2 data. | Secondary: Breadth (0-5) |
|-------------------------|----------------|--|--------|---|--|--|
| P6 (MOS1+MO S2) | PP080 | 18mer peptides overlapping (41) by 11aa spanning the 5` half of P3 of both Mosaic-1 and Mosaic-2 | 2ug/ml | 4 | Examining breadth at the subpool level. Also, a second an independent check of Mos-1/Mos-2 data. | Secondary: Breadth (0-5) |
| Clade B Env | PP004 | Overlapping 18mer peptides spanning Clade B Envelope (year) | 2ug/ml | 4 | Not in vaccines. i) Descriptive analysis of whether vaccination has any nonspecific effects on ENV-specific T cell responses in ELISpot ii) Immunodominance analysis | Exploratory: (SFU/10^6 PBMC) |
| Clade B Nef/Acc | PP081 | Overlapping peptides spanning Nef, Rev, Tat, Vif, Vpr, Vpu | 2ug/ml | 4 | Not in vaccines. i) Descriptive analysis of whether vaccination has any nonspecific effects on ENV-specific T cell responses in ELISpot ii) Immunodominance analysis | Exploratory: (SFU/10^6 PBMC) |
| Junctions | PP082 B | Overlapping peptides spanning junctional sequences between the 6 HIV regions of the vaccine immunogens across the four immunogens inC1, C62, M3,M4 | 2ug/ml | 4 | In the vaccine immunogen, but not HIV-specific. Descriptive analysis as to whether vaccination induced T cell response to these regions | Exploratory: (SFU/10^6 PBMC) |

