4.1.8 Test Size and Confidence Levels

For all primary and secondary endpoints in this trial, 95% confidence intervals will be computed for all relevant estimates. Because this is a Phase I study with a small sample size and exploratory endpoints, results will be presented without adjustment for multiple comparisons or multiple testing of endpoints. Given the small sample size, exact methods that do not rely on large sample assumptions will be used for statistical inference and will always be presented with corresponding descriptive statistics and/or data visualization. Type-I error control (alpha) for all comparisons will be set to 0.05, and all tests will be two-sided.

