Design: Empirical power calculated by simulating 10,000 random samples, assuming log-transformed HIV-specific T-cell response follows a normal distribution. The effect under the alternative hypothesis was a GMR of 2 on the raw T-cell response measures. An SD of 0.8 for both pre- and post-vaccination measurements was assumed to calculate power. This assumption was based on previous, log-transformed HIV-specific T-cell response data, which gave a between-participant SD of 0.8 at baseline. A within-participant Pearson correlation of between r = 0.8 and r = 0.9 was assumed between paired log-transformed HIV-specific T-cell response measures.

Design: Empirical power calculated by simulating 10,000 random samples from a normal distribution. Assume a p=90% or p=87% probability that the difference in HIV-specific T-cell response for any given participant in the **C1C62-M3M4** arm is higher than any given individual in the **C62-M4** arm.

Statistical Test for Power: Two-Sided Exact Wilcoxon Signed-Rank Test to achieve exact p-value < 0.05

Statistical Test for Power: Two-Sided Exact Wilcoxon Rank-Sum Test to achieve exact p-value < 0.05

| Sample Size: N=8 (per arm) | Sample Size: N=8 (per arm) |
|----------------------------------|----------------------------|
| Empirical Power: | Empirical Power: |
| >95% (within-individual r = 0.9) | 90% (p=90% effect size) |
| >80% (within-individual r = 0.8) | >80% (p=87% effect size) |

Table 5: Power for detecting differences in T-cell breadth between arms.

Aim: Determine the statistical power necessary to detect a change in T-cell breadth (T cell breadth is defined as the number of reactive HIV subpools as described in Section 8.2) between vaccine arms

Data: For the C62-M4 and C1C62-M3M4 arms, we anticipate that vaccination will induce a change of breadth (the detection of a new reactive T cell epitope) ranging from 0-3 epitopes and 2-6 epitopes, respectively. We anticipate that C62-M4 will induce a change in breadth with the following frequency distribution: 0 (20% of participants), 1 (50%), 2 (20%), and 3 (10%). We anticipate that C1C62-M3M4 will induce a change in breadth with the following frequency distribution: 2 (30% of participants), 3 (40%), 4 (15%), 5 (10%), and 6 (5%). Note, that these estimates are based on previous empirical

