mapping of HIV-specific T cells against 'individual' peptides spanning Gag/Pol regions corresponding to the HIVconsvX immunogens [1]. In the breadth analysis here, we first examine change of breadth to subpools (n=5) of peptides spanning the HIVconsvX immunogens. Future exploratory analyses will examine change in breadth at the individual peptide level.

Design: Calculate empirical power by simulating 10,000 random samples (as described in Data) from the **C1C62-M3M4** cohort. Compare this generated sample to **C62-M4** only, assuming zero change in T-cell breadth. Count the number of successes (p-values < 0.05).

Statistical Test for Power: Two-Sided Exact Wilcoxon Rank-Sum Test to achieve exact p-value < 0.05

Sample Size: N=8 (per arm)

Empirical Power: 95%

6 Primary Outcome: Safety

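### The between-arm breadth test subtracts baseline breadth but does not adjust for it, which costs power on a 0-5 scale; how much depends on baselines that the documents do not give

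*SAP*

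**What the plan says.** SAP 8.2 (Outcome 2.2) and 8.3.C.e compare the arms on the Day 56 count of reactive subpools minus the pre-vaccination count. The test is stated as "an exact two-sided Wilcoxon rank-sum test will be used for between-arm comparisons", and protocol 10.7.4.3 uses the same test. SAP 4.1.8 fixes the error rate: "Type-I error control (alpha) for all comparisons will be set to 0.05, and all tests will be two-sided". SAP Table 1 gives the range of breadth as 0 to 5.

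SAP 8.3.C scores a subpool as positive at baseline if it is reactive at any pre-vaccination visit, so each participant has a baseline breadth. No covariate or stratification is planned, and the upper limit of the scale is not discussed.

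On power, protocol 10.7.4.4 says that 8 "evaluable participants per treatment arm provides 95% power to detect a difference between arms". The assumed gains are 0 to 3 epitopes for C62-M4 and 2 to 6 for C1C62-M3M4. SAP Table 5 repeats them and states that they come from individual-peptide mapping, whereas the analysis uses five subpools.

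**The concern.** A participant who starts with B reactive subpools can gain at most 5 - B. The only baseline information in the documents is at epitope level: protocol 2.2.3.1 reports an average of 3 targeted epitopes within the immunogen regions, range 0 to 6, in an earlier cohort on ART. If baselines in this trial are similarly above zero and vary, the change score carries baseline variation that a covariate could remove. With 8 per arm, chance differences in baseline breadth add noise to the comparison. Changes confined to a few integers also produce many ties, which makes an exact rank-sum test conservative.

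This is the planned between-arm test of the trial's breadth hypothesis, that the bivalent regimen broadens responses more than the monovalent one. If its power is low, a null result says little about that hypothesis.

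**Working it through.** **1. The plan's own figure.** Inputs from protocol 10.7.4.4 and SAP Table 5: 8 v 8, two-sided 0.05.
- C62-M4 gains of 0/1/2/3 with probability 0.20/0.50/0.20/0.10: mean = 0.5 + 0.4 + 0.3 = 1.2.
- C1C62-M3M4 gains of 2/3/4/5/6 with probability 0.30/0.40/0.15/0.10/0.05: mean = 0.6 + 1.2 + 0.6 + 0.5 + 0.3 = 3.2.

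Over 10,000 simulated datasets, an exact rank-sum with midranks over all C(16,8) = 12,870 allocations has 95.2% power. The stated 95% reproduces. The SAP's design sentence instead sets the comparator by "assuming zero change in T-cell breadth". That gives about 100%, so the 95% belongs to the protocol's description.

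**2. The tests compared.** B is baseline count, Y is Day 56 count, and ranks are midranks over all 16 participants.
- Planned: W = sum of ranks of (Y - B) in one arm.
- Quade: regress rank(Y) on rank(B) ignoring arm; T = sum of residuals in one arm.
- Permutation ANCOVA: permutation test of the arm effect with the raw baseline count as covariate.

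The first two take their p-value from all 12,870 allocations.

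**3. Table 5 gains mapped to the 0-5 endpoint.** Assumptions: each epitope falls in a subpool with probability proportional to the peptide counts in SAP Table 1 (64, 38, 42, 54, 41; total 239), no reactivity is lost, and baseline averages 3 epitopes. There were 4,000 datasets per row (1,000 for permutation ANCOVA).

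| Baseline epitopes | Mean change, C62-M4 / C1C62-M3M4 | Rank-sum on change | Quade | Permutation ANCOVA |
|---|---|---|---|---|
| Binomial(6, 0.5) | 0.58 / 1.29 | 32.0% | 42.7% | 45.4% |
| Uniform 0-6 | 0.62 / 1.39 | 29.7% | 44.8% | 48.8% |
| All exactly 3 | 0.55 / 1.24 | 31.7% | 40.5% | 41.4% |

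The gain is 9 to 15 points for Quade and 10 to 19 for permutation ANCOVA. Monte Carlo standard error is at most 0.8 points (1.6 for ANCOVA). Repeat simulations of the first two rows gave 28-33% for the rank-sum and 42-49% for the adjusted tests. With a lower baseline averaging 1.5 epitopes, one repeat gave 50.9% against 61.0% (Quade), a gain of about 10 points.

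**4. A different assumption.** Take the stated gain g as subpools, capped: change = min(g, 5 - B), with B Binomial(5, q).

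| Mean B | Rank-sum | Quade | Gain (points) |
|---|---|---|---|
| 0.5 | 95.4% | 93.8% | -1.6 |
| 1.0 | 94.2% | 92.7% | -1.5 |
| 1.5 | 88.5% | 91.0% | +2.5 |
| 2.0 | 78.7% | 87.8% | +9.1 |
| 2.5 | 63.8% | 80.6% | +16.8 |
| 3.0 | 40.0% | 69.9% | +29.9 |

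If all baseline counts are identical, Quade reduces to the rank-sum and the gain is zero. A rank test on baseline residuals loses about 3 points at the lowest baseline (92.0% v 95.4%).

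**5. How much is tie relief.** Under the null in the step 3 model with uniform baseline, actual size was 2.4% and 3.5% for the rank-sum, against 5.1% and 4.8% for Quade (nominal 5%, within simulation error). Forcing all tests to exactly 5% by randomisation, as a diagnostic only, in a separate run of 2,000 trials:
- Binomial baseline, Quade: gain as run 43.2 - 32.6 = 10.6 points; at equal size 44.2 - 40.7 = 3.5.
- Uniform baseline, Quade: 41.9 - 29.4 = 12.5; at equal size 42.4 - 37.4 = 5.0.
- Uniform baseline, regression version: 46.0 - 29.4 = 16.6; at equal size 48.1 - 37.4 = 10.7.

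Between (16.6 - 10.7)/16.6 = 36% and (10.6 - 3.5)/10.6 = 67% of the gain in these runs is relief from ties. With every participant at exactly 3 baseline epitopes, nearly all of it is: 6-8 points as run, under 1 at equal size.

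**The case against.** The strongest reply is that the planned test is legitimate and matches the stated endpoint, which is change in breadth. Under randomisation the rank-sum on change holds its error rate, and chance baseline imbalance adds variance, not bias. A reader might infer that baseline is ignored or that the test is wrong. The documents do not support that: baseline is measured and subtracted. This part of the reply stands.

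The second reply is that the size of the gain rests on assumptions. The 3 epitopes come from individual-peptide mapping in another cohort. SAP 8.3 uses stricter pool-level criteria (above 20 SFU, at least four times mock, no zero wells). It also asks for post-vaccination reactivity at more than one visit but baseline reactivity at any one, so losses are possible. This also stands, and it rules out a single figure. A check in which 20% of baseline reactivities were lost gave similar gains, so the direction does not depend on the no-loss assumption.

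Third, this is a secondary endpoint in a Phase 1 trial. Protocol 10.7.1 puts the emphasis on description and warns that meaningful effects may go undetected. That limits the importance of the point, but does not argue against a better exact test that needs no new data.

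**Conclusion.** The point holds as a loss of efficiency. In the model closest to the documents' figures, the rank-sum on change has about 28-32% power and an exact baseline-adjusted permutation test about 41-49%, a gain of roughly 9-19 points. Across other baseline assumptions the gain runs from about -3 points (baselines at or near zero) to about +30 (many participants near the ceiling). It is zero for Quade if baselines are equal. Part of the gain is relief from the tied rank-sum's actual size of about 2-3%, and not information recovered from baseline.

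These figures rest on assumed subpool-level baselines, random placement of epitopes and, in the tabulated runs, no loss of reactivity. They keep all 16 participants, so they do not model the SAP 8.3.C.e instruction to drop values equal to the hypothetical value.

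A reader might also infer that adjustment restores the planned power. It does not. The stated 95% uses epitope gains that the endpoint cannot take: a gain of 6 subpools is impossible and a gain of 5 requires a baseline of zero. The fall from 95% to about 30% in this model is a separate and larger problem.

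**What to change.** In SAP 8.2 (Outcome 2.2) and 8.3.C.e, and in protocol 10.7.4.3, name one between-arm breadth test: a Quade rank ANCOVA of Day 56 breadth on pre-vaccination breadth, with a two-sided p-value from the full permutation distribution (12,870 allocations for 8 v 8, or all allocations at the actual arm sizes). Keep the exact rank-sum on change as a supportive analysis. Name only one adjusted test, because offering a choice of adjusted methods would leave the analysis open. Make the change before arm-specific results are reviewed, in line with SAP section 9.

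The cost is a few lines of SAP text and code, and up to about 2-3 points of power if baselines prove low. The permutation version keeps to the SAP 4.1.8 commitment to exact methods.
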